
#### 5.2 Summary of current evidence

There is a substantive literature reporting the relationship between sperm DNA integrity and dysfunction. Several key studies show that DNA packaging and fragmentation anomalies influenced by sperm DNA damage are strongly associated with CPR, LBR and pregnancy loss in IVF procedures. For ICSI, the only clear association is with pregnancy loss supporting the existence of genotoxic damage that is hidden from conventional tests. Hence any improvement in ICSI that allows the selection of sperm with reduced damage is to be encouraged. Additional benefits of increasing success rates include a reduction in the potentially harmful maternal ovarian hyperstimulation protocols that are an integral part of the ICSI cycle (fewer cycles) and a concomitant reduction in the costs of ART procedures. For example, a modest 8% improvement from the current 24% to 32% measured as live births at >34 weeks' gestation per cycle would lead to a corresponding 10% improvement in successful live births overall (based on an average of 1.3 cycles per patient) from 30.6% now to 40.6% in future. One effect of this could be to reduce cycles while maintaining current success rates (losing 1 cycle in five overall). Hence, over the current 25,000 ICSI cycles performed per annum in the UK this would represent an annual NHS saving of more than £17.5m (based on average costs of £3500 per ICSI cycle). Maintaining the current cycle average could see even greater longer term savings in relation to the knock-on effects of pregnancy failure to NHS costs.

Sperm genomic integrity is important because work conducted in our and in other laboratories has shown that in human and mouse sperm, the genome is carefully and systematically organised in the nucleus into distinct geographical domains. These studies showed that some domains are enriched in histones that can account for their hitherto unexplained

persistence in sperm nuclei alongside the more abundant protamines. Intriguingly, histone-bound sperm chromatin domains are enriched in developmental gene sequences expressed in early embryogenesis. We postulate that these developmentally significant domains are critically relevant for subsequent early embryogenesis and that DNA damage located therein could account for the early pregnancy failure observed after both IVF and ICSI based procedures. We have evidence that the form of paternal DNA damage that may be responsible for such early pregnancy failure involves nucleotide oxidation. This particular form of DNA damage is only revealed after treating the DNA with an enzyme that converts extant oxidised purines (such as 8-OHdG) into DNA strand breaks . Such damage is probably caused by reactive oxygen species (ROS) gaining access to chromatin domains that should normally be protected but are exposed due to anomalous packaging defects at critically important locations. The potential genotoxicity of oxidised nucleotides, however, would be hidden to the investigator because the strand breaks that are normally detected in assays of such damage would only be revealed following gamete fusion.

## **5.2.1** Is DNA damage the link connecting sperm chromatin integrity and pregnancy failure?

[figure not shown]
It is highly likely that some important regions in sperm chromatin  are sensitive to DNA damaging agents . In the most severe forms of DNA packaging defects such as complete absence of protamine (as in mouse knockout models, for example), embryo lethality is the norm. Moreover, even small imbalances in the balance of DNA packaging proteins in sperm have deleterious effects on fertility. Hence, there are clear connections between stoichiometric chromatin imbalance and DNA fragmentation, suggesting that problems with one are reflected by complimentary problems in the other. During spermiogenesis, when the paternal genome is being repackaged to fit a much smaller nucleus, any deficiencies in the packaging process are likely to leave some DNA sequences more exposed to damaging ROS than others. While it may be the case that we cannot do anything about such types of DNA damage in standard IVF procedures, it should be possible to eliminate these damaged sperm from the pool prepared for ICSI based procedures and by so doing, reducing pregnancy loss and correspondingly increasing LBR.

### 5.3 Work leading to the study

## **5.3.1** The potential for hyaluronan binding to discriminate and select for sperm with high chromatin integrity.

[figure not shown]
In the clinic, wherever possible, ART makes use of sperm isolated through either DGC or swim-up processing (and occasionally both). This helps to obtain the better quality sperm for

subsequent IVF or ICSI (WHO Manual) although even selected sperm are not entirely free of DNA fragmentation as indicated by recent studies  see Figure 2B. Hyaluronic acid or hyaluronan (HA) is the major glycosaminoglycan secretion of the cervix and the cumulus-öopherus complex. Sperm reaching these surfaces can bind to HA and subsequent hyperactivation facilitates their penetration to the zona pellucida of the egg. Work by Huszar and colleagues showed that immature sperm with excessive cytoplasm had higher rates of aneuploidy, lowered cytoplasmic maturity and a dysfunctional ability to bind HA. Pelleted sperm are more homogeneously normal in this critical respect. The cytoplasm-rich, poorly HA-binding sperm of DGC interface sperm also have poorer morphology and motility and exhibit higher rates of DNA damage.

**Figure 1**. Ability of sperm to bind spots of HA on glass substrates. Panels (a) and (b): fluorescence micrograph of live-dead staining of sperm in contact with HA-coated 'spot' before (a) and after (b) washing to remove non-adherent cells. Panels A and B: fluorescence (A) and brightfield micrograph (B) of adherent sperm. Note the absence of dead sperm in A and the tip of the handling pipette in B. Live-dead assay used cyber green (living) and propidium iodide (dead) in combination. From Huszar, 2007 (Ref 50).

Prinosilova et al obtained an over threefold greater number of strict Tygerberg sperm (a rigorous test for normal sperm morphology) following exposure of highly abnormal semen samples to a HA-coated substrate (Figure 1). Using a similar selection system, Sati et al showed that HA-binding sperm had more compact chromatin, lower DFR and less residual cytoplasm than non-binding sperm.

### **5.3.2** Evidence of the beneficial effect of HA selection on pregnancy outcome.

In many clinics, polyvinylpyrrolidone (PVP) is normally used to slow sperm down sufficiently for capture by the clinical embryologist. Two clinically relevant studies have reported on effects following a HA-selection procedure for ICSI. Parmegiani et al  obtained higher numbers of Grade 1 embryos for transfer following ICSI with HA rather than PVP-selected sperm (36% versus 24%) and an improved LBR (23% vs 18%). A more recent and larger randomised study used a fully developed HA based sperm selection (PICSI) versus PVP procedures in 802 ICSI cycles (Table 2 This study showed a 13% increase in CPR [N = 121]) using HA versus PVP selected sperm with a corresponding drop in miscarriage rate (14.1% vs 3.8%; N = 168). Closer examination of the trial data indicates a more general 5-10% improvement in CPR if the data are stratified according to the DGC washed HA binding score (obtained prior to PICSI selection), with lower scores (≤65%) giving the best results. This may explain why CPRs in HA versus PVP arms were balanced before stratification according to the post-DGC washed HA binding score, while pregnancy failure rates fell by 6% (Table 2). The US trial has now reported LBR, and provided strong supporting evidence for HA selection reducing early pregnancy failure . Our trial will seek to confirm this as well as contributing data on LBR, miscarriage rate and notably to a better understanding of the basic underlying mechanistic of action of HA sperm selection.

[figure not shown]
HBS	Implantation	CPR (%) at	MCR (%) based on C P with fetal
	rate (%) at 4	6-8 wks	sac (6 wks) less fetal heartbeat
	wks		(8 wks)
All scores	32.2 / 33.5 	47 .8/47.3 	10.0 / 4.3247
>65%	34.8 / 37.9	51.1/46.2 	7.8 / 5 .9 
≤65%	30.7 / 37.4	37.9/50.8 	18.5 / 0 

**Table 2**. Final output from the US clinical trial on PVP (blue) versus PICSI (green) based selection. Sample numbers are shown in superscript. HBS refers to the hyaluronan binding score for DGC washed sperm. From Worrilow et al, . Please see text for more details. Numbers in superscript indicate sample size.

## 5.4 The study rationale

## 5.4.1 Mechanistic aspects

Protamines are the principle DNA binding proteins of human sperm chromatin, comprising at least 85% of the mass of the paternal genome . Histones constitute the remaining 10-15%; hence sperm chromatin exists in a complex arrangement of protamine and histone-bound DNA (Figure 3). As indicated above, our work as supported by independent studies has provided strong experimental evidence for differential DNA packaging in sperm nuclei into high (protamine) and low (histone) compaction domains that will have differing susceptibilities to potential DNA damaging agents (Figure 3).

proteins during spermatogenesis. Histories are acetylated (Ac) prior to their removal. Although it is not known whether the remaining histories are there by design or as a residue of this shift, their presence introduces a 'weakness' into the overall chromatin structure that may be more vulnerable to naturally or iatrogenically induced damage. From Oliva, 2006 (Ref 36).

Our evidence suggests that the less compact and hence more susceptible domains are enriched in regulatory sequences for genes that are important in early embryonic development. As DNA is differentially packaged into domains that reflect a clear organisational framework, then we hypothesize that sperm DNA fragmentation reflects alterations in the packaging of sperm chromatin that leaves some critical DNA sequences more exposed to oxidative damage than others. We aim to test the hypothesis that PICSI more robustly selects for sperm with good chromatin integrity, and correspondingly low DNA damage than manual selection normally permits. Although this suggests that PICSI (or other HA-based selection procedures) may best be applied among semen samples that are of particularly low quality, there is no reason why it could not be applied more widely in IVF-ICSI if the evidence from this study supports its efficacy. While not the purpose of this study, HA-based sperm

selection could potentially be extended into standard IVF procedures if methods are developed to restore the fertilisation potential of pre-HA bound sperm.

[figure not shown]

Figure 4. A Hydak HBS slide showing twin chambers. B. Photomicrographs of time lapse image from sperm added to chamber at 0 and at 30s. Sperm stained with Cyber green. The degree of 'wiggle' reflects sperm motility. C. PICSI plate showing channels into which sperm suspensions are introduced. Sperm migrate towards the hyaluronic coated areas at one end of each channel where they bind. From Biocoat original datasheets.

#### 5.4.2 Interventional Aspects

The 2010 WHO manual on semen analysis has altered the definition of a 'normal' fertile sample because the relationship between sperm 'normality' and the ability to achieve a pregnancy following 12 months of unprotected intercourse is far from obvious. The emerging consensus based on some older observations that remain just as valid today is that the morphology of sperm recovered from the endocervix or zona pellucida is a better indicator of their functionality than is morphology based on raw semen analysis. Hence, the emphasis now is on identifying those sperm in the ejaculate that can progress through the female genital tract to reach the endocervical mucus and beyond to the egg. Using the WHO guidelines, the range of percentage 'normal' values for both fertile and infertile men is likely to be between 0-30%, with few samples exceeding 25% normal spermatozoa. Such low values inevitably produce low thresholds. For

example, limits and thresholds as low as 3–5% normal forms have been found in studies of invitro fertilisation, intrauterine insemination and in-vivo fertility. Similarly, the range of percentage motile sperm found in even 'pristine' spermatozoa in the ejaculates of fathers can be very wide (8–25%). Hence, none of the aforementioned parameters are particularly helpful in providing a useful definition of sperm 'normality'. What seems to count most is the sperms' ability to reach the egg's zona, which supports the contention that a prior binding to the HA matrix of the cumulus is a prerequisite. This is why sperm selection for IVF in general and ICSI in particular needs improved standards that do not rely on or at least minimise possible adverse effects of subjective decisions. In clinical practice, both the PVP and PICSI processes make use of special chambers into which DGC or swum-up processed sperm are introduced (Figure 4c). Neither process is inherently any more difficult to perform than the other and an embryologist used to PVP based processing can be quickly trained to use PICSI instead.

## 5.4.3 Risks and benefits

Hyaluronan is a natural polymeric secretion of the cervical mucus and cumulus-oopherus complex and so poses no known risks to the egg or zygote. PICSI – HA based selection system has been CE approved for use and no risks have been identified by the manufacturer. However as a precaution against possible adverse effects of intervention such as early pregnancy loss or preterm labour we will conduct a safety monitoring interim analysis. PVP is an inert synthetic polymer that is used extensively in the food and pharmaceutical industries with no known adverse side effects. It is used in almost every ACU as a viscous retardant of sperm motility, making it easier for a skilled practitioner to isolate and prepare a single sperm for ICSI. The advantage of switching to hyaluronan is likely to be threefold.

**Firstly**, sperm bind to HA, effectively immobilising them long enough to be picked up. **Secondly**, HA is thought to work by selectively binding sperm of a higher quality allowing the embryologist to wash away non-adherent sperm before the choice of sperm for pick-up is made.

**Thirdly**, although the trained embryologist can be very good at selecting the 'right' sperm for injection HA should remove any subjective operator selection and allow consistent objective selection of the 'right' sperm for injection.

The main benefits expected of switching to HA are a decrease in early pregnancy loss and a subsequent increase in LBR at normal term. We consider that HA selection will be beneficial to couples where semen quality is too poor for IVF and may also have a significant benefit for older women with poorer quality eggs that have a decreased potential to repair sperm DNA damage. Couples participating in this research study will benefit the community by increasing the knowledge base of clinical and scientific improvements in the effectiveness of ICSI procedures.

## 5.4.4 Justification

- There is a need to increase LBR at term for IVF and IVF-ICSI patients by reducing fertilisation failure and miscarriage rate.
- Male fertility is thought to be declining through a reduction in sperm counts across the globe since WWII .

- The number of IVF and ICSI procedures is rapidly increasing and in particular, ICSI is being increasingly used for reasons other than treating male infertility (it now accounts for >50% of all IVF cycles), hence the selection of high quality sperm becomes a more urgent priority.
- Average LBR for IVF and IVF-ICSI have reached a plateau at 24% (although success rates vary widely across clinics and younger couples are generally more successful).
- Lower rates of fertilisation and higher rates of pregnancy loss following ICSI procedures are likely to generate higher costs as its use widens beyond treatment for male infertility. Wider use of ICSI without appropriate and adequate safeguards could lead to a future increase in the incidence of deleterious gene lesions in the wider population.
- The largest clinical trial so far, involving nine US centers has shown efficacy for PICSI in increasing CPR (10%) and a corresponding reduction in miscarriage rate (10%). A smaller Italian trial reported an encouraging 5% improvement in LBR following HA-based selection (using a non-optimised HA containing solution).
- Of the two commercially available HA-based selection systems, PICSI can be introduced into the ART procedure with minimal training and without any additional intervention and is the only product shown so far to have clinical efficacy in improving CPR.
- HA-based selection overcomes the highly subjective assessment of sperm quality used by the practicing embryologist to choose the 'right' sperm for injection.

## 6. AIMS AND OBJECTIVES

## The main aims of this EME proposal are two-fold:-

- To show that the substitution of the usual polyvinylpyrrolidone (PVP) based sperm selection step with a hyaluronic acid (HA) binding step (PICSI) in an assisted reproduction setting can significantly improve the LBR over conventional ICSI procedures.
- To assess how the chromatin state of PICSI selected versus PVP selected sperm corresponds with HBS, CPR, LBR and pregnancy loss.

### 6.1 Objectives

## 6.1.1 Primary Objectives

## 6.1.1.1 *Clinical:*

To determine the efficacy of hyaluronan-selected IntraCytoplasmic Sperm Injection (PICSI) versus PVP ICSI in a rigorous randomised controlled clinical trial of participants where the primary outcome measure will be live birth rate (LBR)  $\geq$ 37 weeks' gestation after ICSI procedure with first fresh embryo transfer.

## 6.1.1.2 *Mechanistic:*

Evaluate if PICSI can compensate for poor sperm quality and investigate HBS in relation to chromatin integrity and LBR. Evaluate the differences in chromatin architecture in DGC washed and pelleted sperm with high and low HBS including any correlation with DNA damage.

## 6.1.2 Secondary Objectives

## 6.1.2.1 *Clinical:*

To determine the impact of PICSI-selected IntraCytoplasmic Sperm Injection (PICSI) versus PVP ICSI on:

- increasing clinical pregnancy (CP) rate based on detection of fetal heartbeat or presence of fetal sac at 6-9 weeks' gestation
- reducing miscarriage rate defined as pregnancy loss after confirmation of clinical pregnancy,
- increasing LBR at <37 weeks' gestation.

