### **11.3 Outcome Data Collection:**

- Biochemical pregnancy rates based on the detection of hCG in the mother's blood or urine.
- Clinical pregnancy rates based on ultrasound scanning (fetal sac and/or detection of heartbeat).
- For the primary clinical outcome: successful live birth ≥37 completed weeks since embryo transfer or last menstrual period.
- For the secondary clinical outcomes:
  - miscarriage, defined as pregnancy loss after confirmation of clinical pregnancy
  - live birth <37 weeks

All of the above will be based on data gathered from the ICSI cycle with first fresh embryo transfer per couple.

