## 13.2.2 Secondary endpoint analyses

The secondary endpoints are the respective proportions of women who:

- experience a clinical pregnancy based on presence of fetal heartbeat or fetal sac at 6-9 weeks' gestation
- experience a clinical pregnancy and miscarry
- experience a clinical pregnancy and proceed to a live birth <37 weeks

These proportions have as their denominator the number of women who are followed up after their first ICSI cycle post randomisation, and as their numerator the number with the respective outcome. The proportions of each will be compared between arms using multivariable logistic regression adjusting for centre and for factors used in the minimisation. An odds ratio with 95% confidence interval will be calculated.

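### The secondary objective seeks more live births before 37 weeks, against the protocol's own rationale, and no planned comparison covers live birth at any gestation

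*Protocol*

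**What the plan says.** Section 6.1.2.1 gives each clinical secondary objective a direction: clinical pregnancy is to rise, miscarriage is to fall, and the third item is "increasing LBR at <37 weeks".

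Section 5.4.3 plans a safety interim analysis "as a precaution against possible adverse effects of intervention such as early pregnancy loss or preterm labour". It describes the main expected benefits as "a decrease in early pregnancy loss and a subsequent increase in LBR at normal term".

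The primary outcome is live birth at 37 weeks or later (6.1.1.1, 7.3, 11.3, 13.1.1.1, 13.2.1). Live birth before 37 weeks is a secondary outcome (11.3, 13.1.2.1). Section 13.2.2 analyses it as the proportion of women who "experience a clinical pregnancy and proceed to a live birth <37 weeks", compared by an adjusted odds ratio with a 95% confidence interval. On the denominator it says: "These proportions have as their denominator the number of women who are followed up after their first ICSI cycle post randomisation". Section 13.6.1 adds an analysis restricted to clinical pregnancies only if the clinical pregnancy rate differs between arms.

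Section 6 gives the trial's main clinical aim as an improvement in live birth rate, with no gestational limit. No objective, outcome or analysis counts live births at any gestation.

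**The concern.** There are two linked faults.

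The first is a contradiction. The objective presents a rise in live births before 37 weeks as something PICSI should achieve. The rationale presents preterm labour as something it might cause, and claims benefit only at term. Preterm labour and live birth before 37 weeks are not identical, but the second is the only preterm measure among the trial's listed outcomes. That measure therefore carries a favourable direction in the objectives while a closely related event is a hazard in the rationale.

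The second is a gap. A rise in births before 37 weeks can arise because more women have a baby, or because the same number have one earlier. A comparison of live birth at any gestation, with its own confidence interval, speaks directly to that distinction and to the aim in section 6. It is not planned. Nor is the preterm proportion among live births.

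At stake is how a rise in births before 37 weeks would be reported. Taken with the objective as worded, it could be presented as a secondary success when it might reflect earlier delivery.

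**Working it through.** **Setting the sections side by side**

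| Section | Live birth or labour before 37 weeks | Direction |
|---|---|---|
| 6.1.2.1 | Effect sought from PICSI | Increase is favourable |
| 5.4.3 | Preterm labour as possible adverse effect; benefit at normal term | Increase is unfavourable |
| 11.3, 13.1.2.1, 13.2.2 | Secondary outcome, two-arm comparison | None stated |

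Only 6.1.2.1 assigns a favourable direction.

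**The plan's own figures.** Section 13.5 gives 3,266 couples for a 5-point improvement at 90% power. I use 24% against 29% (24% is the average rate in 5.1) and assume two-sided alpha of 0.05, which the protocol does not state:

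n per arm = (1.960 + 1.282)² × (0.24×0.76 + 0.29×0.71) / 0.05² = 1,632.01, rounded up to 1,633; 2 × 1,633 = 3,266.

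This reproduces the figure. Section 13.4.1 allows 10% loss: 3,730 × 0.9 = 3,357, or about 1,678 per arm, used below.

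**Case A: births move earlier, total unchanged.** The protocol gives no preterm rate. I assume 24% term live birth on PVP-ICSI and 2%, 3% or 4% of women with live birth before 37 weeks. PICSI moves 2 points from term to preterm.

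Odds ratio = [p1/(1−p1)] / [p0/(1−p0)]. The variance of its logarithm is the sum of the reciprocals of the four cell counts. Power = Φ[(|p1−p0| − 1.96·SE₀)/SE₁], with SE₀ pooled and SE₁ unpooled.

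| Comparison | Odds ratio (95% CI at expected counts) | Power |
|---|---|---|
| <37 weeks, 2% → 4% | 2.04 (1.34 to 3.11) | 92% |
| <37 weeks, 3% → 5% | 1.70 (1.19 to 2.43) | 84% |
| <37 weeks, 4% → 6% | 1.53 (1.12 to 2.10) | 76% |
| ≥37 weeks, 24% → 22% | 0.89 (0.76 to 1.05) | 28% |

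Worked line for the term outcome: SE₁ = √[(0.24×0.76 + 0.22×0.78)/1,678] = 0.01453; 0.02/0.01453 = 1.38; Φ(1.38 − 1.96) = 0.28 (SE₀ is practically equal).

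If only 1 point moves, the <37-week odds ratio is 1.26 to 1.52 with 29% to 46% power, and the term odds ratio is 0.95 with 10% power. If 3 points move, the figures are 1.81 to 2.58 with at least 97% power, and 0.84 with 55% power.

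**Case B: all live births rise in proportion.** Term goes from 24% to 29%, a factor of 0.29/0.24 = 1.208. Births before 37 weeks go from 2% to 2.42% or from 4% to 4.83%. Their odds ratio is 1.21 to 1.22, with no change in preterm risk per live birth.

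**What the two added measures show** (4% starting rate)

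- Any-gestation live birth. Case A: 28% in both arms, with a confidence interval of about ±1.96 × √(2×0.28×0.72/1,678) = ±3.0 points around zero. Case B: 28% → 29% + 4.83% = 33.8%.
- Preterm share of live births. Case A: 4/28 = 14.3% → 6/28 = 21.4%. Case B: 4/28 = 14.3% → 4.83/33.83 = 14.3%.

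The <37-week odds ratio is above 1 in both cases. The added measures differ between them.

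**The case against.** The best defence is that the faulty direction is one word in one bullet. The sentence introducing the list speaks of determining impact, and the operative outcome and analysis text is neutral. This stands, and it confines the contradiction to the objective. A reader might infer that a rise in births before 37 weeks would automatically count as efficacy, or that the objective would then be formally achieved. The protocol does not support this. It has no rule for declaring a secondary objective achieved, the analysis has no favoured direction, and section 13.6.1 gives primary analyses more weight.

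A reader might also infer that the planned outcomes cannot distinguish more births from earlier births. That goes too far. The two strata are mutually exclusive and together cover all live births, their denominators are nearly the same (13.2.1, 13.2.2), and gestational age at birth is collected (section 11 schedule). A shift appears as term down and preterm up, a general gain as both up. Total live birth follows by addition. What is missing is a planned estimate with its own interval, which matters because the term loss in a shift is poorly powered.

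Safety oversight also exists. Section 5.4.3 plans a safety interim analysis partly because of preterm labour, and the data monitoring committee may see unblinded data and advise stopping (11.5, 15.4.2). An excess need not go unnoticed. This does not correct the stated objective or supply the missing comparison in the final analysis.

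Finally, the documents offer no basis for a 2-point shift. That is fair: the figures illustrate sensitivity and do not forecast an effect of PICSI.

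**Conclusion.** The point holds in a limited form. Section 6.1.2.1 contradicts section 5.4.3 on the direction of birth before 37 weeks, and the error lies in the objective only. No planned analysis estimates the effect on live birth at any gestation, although the data for it are collected.

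The practical size depends on assumptions the protocol does not supply: 24% term live birth, 2% to 4% preterm live birth, about 1,678 women per arm, two-sided alpha of 0.05, and a 2-point shift. Under these, the change in the direction the objective favours would more likely than not reach significance (76% to 92% power), and the matching loss on the primary outcome more likely than not would not (28%). With a 1-point shift neither comparison is well powered. The sample size is unaffected. The matter deserves correction because it concerns how a secondary result would be interpreted. It does not undermine the primary analysis.

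**What to change.** - In 6.1.2.1, remove the word that gives live birth before 37 weeks a favourable direction, and state it as a safety outcome with none assumed.
- In 6.1.2.1, 13.1.2.1 and 13.2.2, add live birth at any gestation as a secondary efficacy outcome, analysed by the same adjusted logistic regression.
- In 13.2.2, report live birth before 37 weeks both per woman, as now planned, and as a share of live births. The share conditions on an event after randomisation, so it should be read beside the per-woman comparison and not in place of it.

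The cost is wording in three sections and one more derived secondary comparison, with the small addition to multiplicity that brings. No new data and no change in sample size are needed.
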